#### 11.3 Reference safety information

In this study the reference safety information (RSI) will be the Summary of Product Characteristics (SPC) ANNEX IV

# 11.4 Information of Adverse Events

The investigator will monitor and systematically collect the AEs related to study medication (ARs) starting from the signing of the Informed Consent Form until the final follow-up visit of each subject.

Also, the investigator will assess and record, in detail, the AR, including the start and dates, the description of the event, severity, course, outcome, and the measures taken (treatments, additional complementary examinations, etc).

The AR will be recorded in the medical history and recorded in the Case Report Form.

The subjects who present an AR will be subjected to relevant follow-up until duration of the same.

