# 6.1.2 Secondary endpoint

Secondary endpoints consist of improvement in the severity of negative symptoms as measured by the change in severity of negative symptoms on the SANS and NSA-4 score over the visits of each period (frame time: baseline visit, week 4, week 12, week 24, week 26, week 30, week 38 and week 50).

- Additionally the following secondary objectives will be evaluated. Functional
  improvement due to the change in general functioning measured by the GAF
  scale score from the beginning to week 24 of each period (frame time:
  baseline visit, week 12, week 24, week 26, week 38 and week 50)
- Safety assessment by measuring the frequency, severity, and relationship with study medication of any adverse event described during treatment. The reasons for withdrawal and / or abandonment of the trial will also be evaluated (if applicable): from the signing of the IC until week 52.

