#### 6.4 Blinding procedures

There are no blinding techniques, as it is an open study. Therefore, no procedure for breaking the blind is applicable either.

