# 9.1 Procedures per visit

The follow-up of the patients in the present study consists of 9 scheduled visits in each period (18 in total). Depending on which arm the patient falls on, the trial treatment will begin in one period or another. That is, if after the randomization of the patient, he falls into the Experimental Arm, the treatment will begin on Visit 2 (Day 1) and will end in week 24, corresponding to period 2 as the TAU treatment period. If, on the other hand, the patient falls into Control Arm, the study will begin with a first TAU period (continues with the treatment according to clinical criteria) and it will be in period 2 when the trial treatment begins (in week 26 of the study).

In this protocol the visits are arranged in chronological order, specifying the week to which each one corresponds.

The following sections detail the procedures that must be carried out at each visit.

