# 9.1.3 Visit 3 (Week 1: day 8 ± 3 days)

- Clinical, cognitive and functional evaluation: SAS
- Dosing and dispensing treatment
- Adherence to treatment
- Review of concomitant medication
- Review of adverse events

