# Adverse Reaction (AR)

An AR is any harmful and unintended reaction to an investigational drug, regardless of the dose administered.

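### Section 11.4 limits adverse-event collection, recording, CRF entry and follow-up to related events, which contradicts the 6.1.2 safety endpoint on any adverse event; followed literally, it would leave that endpoint underivable

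*Protocol*

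**What the plan says.** Section 11.4 sets the scope of adverse-event data in four sentences, all limited to related events:

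- Collection: "The investigator will monitor and systematically collect the AEs related to study medication (ARs", from consent to the final follow-up visit.
- Detailed recording: dates, description, severity, course, outcome and measures taken, for the AR.
- CRF entry: "The AR will be recorded in the medical history and recorded in the Case Report Form".
- Follow-up: "The subjects who present an AR will be subjected to relevant follow-up until duration of the same".

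Section 11.2 gives the term a narrow meaning: "An AR is any harmful and unintended reaction to an investigational drug, regardless of the dose administered". The same section defines an adverse event irrespective of relatedness.

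The secondary endpoint in 6.1.2 is wider: "Safety assessment by measuring the frequency, severity, and relationship with study medication of any adverse event described during treatment", over a span from consent to week 52. Section 9.1 lists "Review of adverse events" at Visit 3 and at every later visit, with no condition on causality. Section 13.4 gives the collaborating researchers the follow-up of adverse events, and 13.5 includes their appearance among the things the monitor checks; neither is limited to reactions.

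Two design features bear on the consequence. On masking, 6.4 states: "There are no blinding techniques, as it is an open study". For patients randomised to start on TAU, 9.1 says "it will be in period 2 when the trial treatment begins (in week 26 of the study".

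**The concern.** An endpoint that counts adverse events of every kind and describes their relatedness needs a record of every event, with causality as one field of that record. Section 11.4 reverses the order: causality is judged first, and only events judged related are written down. An investigator who knows the treatment makes that judgement.

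Under that rule the frequency of any adverse event is not available, and relatedness has a single value by construction. The loss would occur at the point of collection, so it cannot be left to an analysis plan.

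A smaller question arises in 11.5. Its first sentence asks the investigator to report within 24 hours those serious events that are both related and unexpected. The next sentence speaks of serious adverse events without either limit.

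**Working it through.** The protocol gives no figure to reproduce here. The check sets the sections side by side and counts visits.

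**1. Scope by section**

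| Section | Subject | Limited to related events? |
|---|---|---|
| 11.4, sentence 1 | Collection | Yes |
| 11.4, sentence 2 | Detailed recording | Yes |
| 11.4, sentence 3 | Medical history and CRF entry | Yes |
| 11.4, sentence 4 | Follow-up | Yes |
| 6.1.2 | Safety endpoint | No |
| 11.2 | Definition of adverse event | No |
| 9 and 9.1 | Review at visits | No |
| 13.4 | Follow-up by researchers | No |
| 13.5 | Monitoring | No |

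Section 11.4 is the only general rule on which adverse events enter the CRF. The sections without a limit refer to review, follow-up or monitoring; none says that unrelated events are entered.

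**2. Effect on the endpoint if 11.4 is followed**

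- Frequency of any adverse event = related + unrelated events. The second term is not recorded, so the sum is unknown.
- Share related = related / (related + unrelated). The recorded data would give related / related = 100%, whatever the truth.
- Severity could be described for related events only.

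**3. Visits at which no vortioxetine reaction is possible**

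- Scheduled adverse-event reviews: Visits 3 to 9 = 7, and Visits 10 to 18 = 9; total 7 + 9 = 16 of 18 visits.
- In TAU-first patients vortioxetine starts at Visit 10 (week 26). The reviews at Visits 3 to 10 come before or at that start: 8 of 16. None can yield a reaction to vortioxetine.
- In vortioxetine-first patients the reviews at Visits 11 to 17 (7 of 16) fall in the TAU period and could yield only late reactions to vortioxetine.

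These counts take the investigational drug in the AR definition to be vortioxetine. Sections 2.10 and 3.4 also list the control antipsychotics under the study products. If reactions to those were counted too, some events on TAU would be recorded, but unrelated events would still be left out.

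**4. Section 11.5 against Annex II**

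- The first sentence of 11.5 covers serious events that are related and unexpected (SUSAR), within 24 hours.
- The next sentence covers serious adverse events that occur from consent to 30 days after the subject concludes or leaves, with no such limit. It can be read as a time window for the first sentence or as a wider duty.
- The Annex II form is for serious adverse events. Its causality options include improbable, excluded and impossible to assess, which 11.2 classes as unrelated for expedited notification. Its study-phase options include screening and washout. Its 24-hour sending instruction has no SUSAR limit.
- Section 11.7 expects the pharmacovigilance unit to notice a rise in expected reactions, which a SUSAR-only report would not send to it.

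The form and 11.7 both favour the wider reading.

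**The case against.** The best defence is that the protocol does not exclude unrelated events throughout. The schedule, 13.4 and 13.5 speak of adverse events in general, and 11.2 defines an unrelated adverse event as a category the investigator assigns. The window in 11.4 opens at consent, before any reaction to vortioxetine is possible, which suggests that AR was loose drafting for adverse events. The CRF is not available, so its adverse-event page may accept unrelated events. This stands as far as it goes: the data loss is conditional on 11.4 being followed. It does not remove the contradiction, because the first sentence of 11.4 spells out the limit and the other three repeat it.

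Concomitant medication with its reason, vital signs, laboratory tests (with reporting of grade 3 or 4 abnormalities) and withdrawal reasons are collected whatever the cause. They replace an adverse-event record only in part.

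A reader might infer three stronger points that the protocol does not support.

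- That a planned vortioxetine-versus-TAU comparison of adverse events is lost. No objective, endpoint or analysis states one. The safety objective in 5.2.2 concerns the safety of vortioxetine through serious events evaluated in relation to it, and 12.2 describes no adverse-event comparison.
- That patient-weeks on TAU measure the loss. They measure exposure, not events missed.
- That serious events judged unrelated escape both the CRF and the pharmacovigilance unit. That requires the narrow reading of 11.5, which the Annex II form makes unlikely.

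**Conclusion.** The contradiction between 11.4 and 6.1.2 is established by the wording and should be corrected. Followed literally, 11.4 makes relatedness an entry filter applied by an unmasked investigator. It allows no recordable vortioxetine reaction in TAU-first patients before week 26, and it leaves the frequency of any adverse event and the related/unrelated split underivable. This rests on one condition, that sites apply 11.4 as written in preference to the wider wording elsewhere. It would be too strong to say that the endpoint certainly cannot be derived.

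The number of events affected cannot be stated: the protocol gives neither an adverse-event rate nor the share expected to be judged related. The wording of 11.5 is a secondary point that needs clarification only and adds no weight to the main one.

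**What to change.** In 11.4, replace the restriction to related events in the first sentence, and the term AR in the three sentences that follow, with all adverse events regardless of causality. State that this holds in both periods and both washouts, and that causality is recorded for each event. This brings 11.4 into line with 6.1.2, 9.1, 11.2, 13.4 and 13.5.

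In 11.5, reconcile the first two sentences with each other and with the Annex II form. State once which serious adverse events the investigator reports to the pharmacovigilance unit, separately from the SUSAR notification that 11.6 assigns to that unit.

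The cost is a wording amendment and somewhat more CRF entry at Visits 3 to 18, where adverse-event review is already scheduled. Whether the CRF page itself needs changing cannot be judged without seeing it.

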#### 11.5 Notification and collection of serious adverse events

The principal investigator or a collaborator must report to the Pharmacovigilance (PhV) department PhV -UICEC-HUVR, all serious adverse events (as defined below), which are related to the treatment and unexpected (SUSAR), within 24 hours (one business day), as of its knowledge (Annex II). Serious adverse events that occur should be reported at any time from the patient's inclusion in the study (defined as the time the subject signs the informed consent) and up to 30 days after the subject concludes or leaves the study. A subject is considered complete either after the conclusion of the last visit or contact (telephone contact with the investigator or a collaborator), as indicated in the protocol evaluation schedule, or after the last dose study medication, whichever occurs later. Withdrawal is defined as the date a subject and / or the investigator determine that the subject can no longer meet the study requirements at any subsequent visits and evaluations.

The investigator will complete and sign the SAEs notification form (Annex II) that will be sent by fax or email to:

Unidad de Investigación Clínica y Ensayos Clínicos Hospital Universitario Virgen del Rocío Dpto. Farmacovigilancia

Email: [contact]

[name] [contact] [contact]

PhV staff will review the form received and, if applicable, will request additional information from the investigator. The researcher will provide information to the promoter or whoever assumes the tasks delegated by the promoter (PhV-UICEC-HUVR Unit) whenever requested and, in any case, when his initial assessment regarding severity or causality changes. To communicate the follow-up information, the notification procedure described previously will be followed.

The PhV-UICEC-HUVR staff will keep a detailed record of all the SUSARs, pregnancies, medications errors, etc. that are communicated to them by the researchers.

Each SUSAR, pregnancy or medication error communicated to the Promoter's PharmacoVigilance team will be reported to the LundBeck laboratory within 24 hours of being aware of it., to the email: [contact]

In the event that a medication error occurs or the investigational medication is used outside of the protocol provided during the study, the investigator will notify the PhV-UICEC-HUVR within 24 hours of being aware of it. The circuit for notification and the form will be the same as for SAEs.

Those AEs that meet the severity criteria described in the definitions section described for this purpose will be considered serious. Clinically significant events that are not life threatening or fatal or require hospitalization may be considered serious adverse drug experiences when, based on sound medical judgment, they may endanger the subject or require medical or surgical intervention to prevent one of the results listed in this definition. Examples of such medical events are allergic bronchospasm requiring intensive treatment, at home or in an emergency unit, blood dyscrasias or seizures that do not lead to hospitalization, or the development of a dependence or substance abuse.

Reporting of laboratory test abnormalities (grade 3 or 4) is also required, unless otherwise noted in this section of the protocol.

#### 11.6 SUSARs expedited notification

The PhV-UICEC-HUVR department is responsible for notifying the AEMPS and the CCAA where the test is carried out, all the SUSAR that are collected in the study, following the procedure indicated in the current legislation.

The maximum period of notification of an individual case of suspicion of SUSAR will be 15 calendar days from the moment in which the promoter has become aware of it. When the suspicion of SUSAR has caused the death of the patient, or endangered his life, the promoter will send the information within a period of 7 calendar days from the moment in which he becomes aware of it. It will complete this information, if possible, in the following 8 days.

This information should include an evaluation of the significance and implication of the findings, including relevant prior experience with the same or similar medications. Likewise, the competent body of each of the Autonomous Communities where the test is carried out must be notified of the suspicions of SUSAR that have occurred in the health centers of their Community. In both cases, the SUSAR notification form will be used for this.

# 11.7 Expedited notification of other relevant safety information

The PhV-UICEC-HUVR department will notify as soon as possible and no later than 15 days after it becomes aware of any information that could modify the benefit / risk ratio of the investigational drug (for example: increase in the percentage of the appearance of the expected AGRs, the AGRs that occur after the completion of a clinical trial, new events related to the conduct of the trial or the development of the investigational drug, any recommendation of the data monitoring committee relevant to the safety of the subjects, etc.).

#### 11.8 Notification to researchers

The sponsor will present the researchers with safety information that could impact the safety of the patients included in the study as soon as possible.

In addition, the investigator will be informed throughout the study about any safety aspect, including protocol modifications due to safety reasons.

#### 11.9 Medication errors

Medication errors are unintentional errors in prescribing, dispensing, administering or monitoring a medication while it is under the control of a healthcare professional or the patient and that may cause harm to the patient.

Misuse refers to a situation in which the medical product is used intentionally in an inappropriate way, not in accordance with the protocol.

Study medication errors and use outside the scope of the protocol will be recorded in the data collection log (CRF), regardless of whether they are associated with an AE / SAE or not. The misuse or abuse will be collected and reported in the security database within 24 hours of the investigator's knowledge of it.

# 11. 10 Pregnancy

Subjects will be instructed to notify the investigator of the pregnancy if it occurs, and the subject will immediately exit the study.

In the event of any pregnancy occurring during the development of the study, the researcher will notify the promoter or whoever assumes the tasks delegated by the promoter within 24 hours of their knowledge. Likewise, the pregnancy will be monitored to document its outcome and the newborn's health status. If the outcome of the pregnancy meets the criteria for SAE or if the newborn presents a serious event, the procedures described for the notification of SAE will be followed.

The notification will be made using the specific SAE notification form which will be sent by fax or email to the same contact that will receive the notifications from SAE. The PhV-UICEC-HUVR department will notify within 24 hours of their knowledge to the LundBeck laboratory.

# 11.11 Periodic Safety Report

During the course of the study, the sponsor will prepare periodic safety reports annually following the recommendations outlined in the ICH E2F guidelines, and they must be submitted to the regulatory authorities and the CRECs involved following the timetable established in the legislation.

#### 12.- STATISTICS

# 12.1 Sample size calculation

As it is a crossover design, each individual acts as their own control, that is, an initial treatment is assigned and after a while it is changed. Therefore, the correct thing to do would be to calculate the sample under the premise of related or paired samples, for this case it would be the dependent samples T test.

The sample size can be calculated in two ways, in the first one, the difference in the means to be detected of the primary variable (BACS), the standard deviations of the treatment change, and the correlation coefficient must be established; while the second is to consider the difference in the means to be detected for the primary variable (BACS) and the standard difference of the differences.

Accepting an alpha risk of 0.05 and a beta risk of 0.2 in a bilateral contrast, 37 subjects are required to detect a difference equal to or greater than 0.5 units. A standard deviation of 1 is assumed. A loss to follow-up rate of 15% has been estimated.

That is, based on the previous parameters, and using a confidence level of 95% and power of 80%, 37 subjects are needed.

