# 6.6 Discontinuation of study treatment and withdrawal of subjects from the study

Premature discontinuation of the clinical trial may occur due to a decision of the regulatory authorities, due to a change in the opinion of the Clinical Research Ethics Committees, due to safety and / or drug problems or indications of ineffectiveness.

It will be considered that there is a voluntary abandonment of the trial due to the refusal of the patient or legal guardian of the same to continue with the treatment or in the study, and the subject will be considered as abandonment immediately after communicating his decision to the Investigator. A patient may discontinue the trial at any time if the person, the legal representative, the investigator or the motorization committee determine that it is not in the best interest of the patient to maintain their participation.

Other reasons for discontinuation include:

- Patients with low compliance with the study drug, below 80%
- Patients requiring hospitalization for worsening psychotic disorder and / or behavioural disturbances associated with psychotic disorder.
- Patients in whom, during the study period, there is a high risk of detected suicide, according to the criteria established by Columbia University according to the risk assessment with the C-SSRS scale.
- Female patients who test positive for urine pregnancy at any time during their participation in the study.
- Any serious adverse event that recommends withdrawal at the discretion of the investigator with the agreement of the monitoring committee.
- The patient decides not to continue with the trial.
- Others: The researcher, as well as the sponsor, reserve the right to interrupt the study at any time for reasonable medical and / or administrative reasons.

Patients who drop out after randomization will not be replaced.

Patients who terminate treatment prematurely will complete an early termination interview and a safety visit.

The patient who has completed the protocol is considered to be one who has completed all the visits included in the 52-week follow-up period.

The interruption of the treatment does not imply that the case is excluded from the statistical analysis. These subjects will be part of the study and will be taken into account when analyzing the data.

There may be other circumstances for the abandonment, which in its case the researcher must make sure that the patient has abandoned the study, and will verify the causes of said abandonment.

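### Section 12.1 claims 80% power for 37 patients with 15% loss; the paired t test it names has about 77 to 78%, if SD 1 is the SD of the within-patient differences

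*Protocol*

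**What the plan says.** Protocol section 12.1 treats the crossover as paired data and names the dependent-samples t test as the basis of the calculation. It then describes two routes to a sample size. The first uses the mean difference, the SDs of the change on treatment and a correlation coefficient. The second uses the mean difference and the spread of the differences.

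The inputs follow. Error rates: "Accepting an alpha risk of 0.05 and a beta risk of 0.2 in a bilateral contrast". Result: "37 subjects are required to detect a difference equal to or greater than 0.5 units". Spread and loss: "A standard deviation of 1 is assumed. A loss to follow-up rate of 15% has been estimated". The section closes by repeating the claim: "using a confidence level of 95% and power of 80%, 37 subjects are needed". It gives no formula, no number of evaluable pairs and no correlation, and does not say which of the two routes was used.

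Section 6.6 adds: "Patients who drop out after randomization will not be replaced". Sections 2.13 and 6.3 say the same.

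The planned number is not the same throughout. Section 2.9 has 37 patients, each receiving both treatments. Section 2.13 has 37 but also 25 per arm. Section 2.16 plans to recruit 50.

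**The concern.** A paired t test on within-patient differences uses only patients with data from both periods. If 15% of 37 are lost and not replaced, about 31 remain, and 31 pairs are too few for 80% power under the test the section names. The 80% is the only justification given for the size of this single-centre trial. A reader of a null result would rely on it to judge what the trial could have detected.

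The meaning of the SD is also open. The section says what each route requires and then gives one SD of 1 without a label. The figure of 37, and any restated power, depend on which SD that is.

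**Working it through.** **Inputs** (section 12.1 unless noted)

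- Test: dependent-samples t test
- Alpha 0.05, two-sided; beta 0.2
- Difference to detect: 0.5
- SD: 1, taken first as the SD of the within-patient differences (an assumption, since the text does not say)
- Loss: 15%; no replacement (section 6.6)
- Randomised: 37

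**Step 1. Reproduce the protocol's figure.** Normal approximation for paired data: n = ((z for 0.975 + z for 0.80) × SD / difference)² = (1.96 + 0.8416)² / 0.25 = 31.40 pairs. Inflated for loss: 31.40 / 0.85 = 36.94, rounded up to 37. The stated figure is reproduced exactly, and loss is handled correctly by dividing by 1 − 0.15. Rounding up to 32 whole pairs first would give 32 / 0.85 = 37.6, that is 38.

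**Step 2. Pairs expected from 37.** 37 × 0.85 = 31.45. In whole patients this is 31 pairs (6 lost, 16.2%) or 32 pairs (5 lost, 13.5%).

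**Step 3. Power of the named test.** For n pairs, the t statistic has n − 1 degrees of freedom and noncentrality 0.5 × √n. Power is the probability that it falls outside the two-sided 5% critical values.

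| Pairs | Power, paired t test |
|---|---|
| 31 | 76.8% |
| 31.45 (unrounded) | 77.5% |
| 32 | 78.2% |
| 33 | 79.5% |
| 34 | 80.8% |
| 37 (no loss) | 84.1% |

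The smallest number of pairs with at least 80% power is 34, and 34 / 0.85 = 40 randomised. With 31 pairs, the difference detectable with 80% power is 0.52.

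**Step 4. Where the gap comes from.** On the normal approximation, power is 80.07% at 31.45 pairs and 79.5% at 31. The gap is therefore almost entirely the use of normal rather than t quantiles, plus a little from rounding to whole pairs.

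**Step 5. Dependence on the meaning of SD 1.** If 1 is instead the SD of the change on each treatment, the SD of the difference between the two changes is √(2(1 − r)), where r is their correlation. The protocol gives no r, so these values are assumptions:

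| r (assumed) | SD of difference | Power at 31 pairs | Pairs for 80% |
|---|---|---|---|
| 0 | 1.41 | 48% | 65 |
| 0.3 | 1.18 | 62% | 46 |
| 0.5 | 1.00 | 77% | 34 |
| 0.7 | 0.77 | 94% | 21 |

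SD 1 per change gives the same result as in Step 3 only at r = 0.5.

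**Step 6. Dependence on the number randomised.** If 50 were randomised (section 2.16, read as an assumption), 50 × 0.85 = 42.5. With 42 pairs the power is 88.6%, above 80%. The restated power must therefore be tied explicitly to 37.

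**The case against.** The best defence is that 37 is not a miscalculation. It follows exactly from the stated inputs by a common planning formula, with loss inflated the right way. The inputs are round planning values, and moving the detectable difference from 0.50 to 0.52 changes nothing in conduct or analysis. This stands: it rules out calling 37 an arithmetic error and makes the point minor. It does not rescue the 80%, because the section names the t test, and neither 31 nor 32 pairs reaches 80% under that test.

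A second defence concerns the SD. Only the first route needs a correlation, none is given, and using SD 1 directly reproduces 37. That points to the second route, with 1 as the SD of the differences. It is a fair inference and the likeliest reading, but the section does not state it, so confirmation is still needed.

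A reader might infer from the correlation table that the trial is badly underpowered. The documents do not support that. A larger shortfall needs SD 1 to be the SD of each change and r below 0.5, and nothing in the protocol indicates either. The same table shows 94% at r = 0.7. A reader might also recompute power for losses above 15%, but the protocol gives no ground for a higher rate.

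**Conclusion.** The point holds as a minor one. With 37 randomised, 15% loss and no replacement, the test named in section 12.1 has about 77 to 78% power, 2 to 3 percentage points below the stated 80%. Three more patients, 40 in all, would be needed to meet the stated figure.

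This rests on two conditions: that SD 1 is the SD of the within-patient difference between the two changes, and that 37 is the number randomised. The section does not settle the first, and sections 2.13 and 2.16 put the second in doubt.

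**What to change.** In section 12.1:

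1. Restate the power: 37 randomised with 15% loss leaves 31 expected complete pairs, and the paired t test then has about 77% power for a difference of 0.5 (80% for a difference of 0.52). Say that 37 came from the normal approximation.
2. Have the sponsor confirm that SD 1 is the SD of the within-patient difference between the change on vortioxetine and the change on TAU, and write that in. If it is the SD of each change, state the assumed correlation and recompute.
3. Reconcile 37 with the 50 patients in section 2.16 and the 25 per arm in section 2.13, so that the power statement refers to one number.

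The cost is a sentence or two in section 12.1 and matching numbers in the synopsis. No extra enrolment is asked for. The only downside is a slightly less favourable stated power.
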